## 5.2 Secondary outcome(s)

### 5.2.1 Secondary outcome 1

To describe effectiveness of durvalumab in combination with platinum–etoposide as first-line treatment for patients with ES-SCLC:

#### Endpoints analyzed:

- Progression-free survival (PFS): The PFS analysis will be based on the programmatically derived RECIST 1.1 using the Investigator tumor assessments. The analysis will be performed using Kaplan Meier plots. Summaries of the number and percentage of patients experiencing a PFS event will be provided along with median PFS and its 95% confidence interval. In addition, the proportion of patients who are progression-free at 6 (PFS 6) and 12 (PFS 12) months will be presented.

A subgroup analysis may be conducted comparing PFS in the following subgroups, assuming sufficient sample size per subgroup: platinum therapy receiving (carboplatin or cisplatin), age ( $\geq 65$ ,  $< 65$ ), gender, performance status, smoking status, CNS metastasis at baseline (Yes/No) and number of chemotherapy cycles (5 or 6 cycles vs 4 or less cycles)

For each subgroup, the HR and 95% CI will be calculated by Cox regression and a log-rank test will be provided.

- Objective response rate (ORR): The ORR will be based on the programmatically derived RECIST 1.1 using the investigator tumor data. Summaries will be produced that present the number and percentage of patients with a tumor response (CR/PR). 95% CI will also be presented.

A subgroup analysis may be conducted comparing ORR in the following subgroups, assuming sufficient sample size per subgroup: platinum therapy receiving (carboplatin or cisplatin), age ( $\geq 65$ ,  $< 65$ ), gender, performance status, smoking status, CNS metastasis at baseline (Yes/No) and number of chemotherapy cycles (5 or 6 cycles vs 4 or less cycles). Results will be compared using Chi-Squared test.

- Duration of response (DoR): DoR will be analyzed using the investigator tumor data in responding patients. Descriptive data will be provided for the DoR in responding patients (continuous data), including the associated Kaplan-Meier curves. In addition, the DoR at 1 year (DoR 12) will be analyzed.

A subgroup analysis may be conducted comparing DoR in the following subgroups, assuming sufficient sample size per subgroup: platinum therapy receiving (carboplatin

or cisplatin), age ( $\geq 65$ ,  $< 65$ ), gender, performance status, smoking status, CNS metastasis at baseline (Yes/No) and number of chemotherapy cycles (5 or 6 cycles vs 4 or less cycles)

For each subgroup, the HR and 95% CI will be calculated by Cox regression and a log-rank test will be provided.

- Overall survival (OS): OS will be analyzed using a Kaplan-Meier plots. Summaries of the number and percentage of patients who have died, those still in survival follow-up, those lost to follow-up, and those who have withdrawn consent will be provided along with the median OS and corresponding 95% CI. In addition, the survival rate at 6 (OS 6), 12 (OS 12), and 18 (OS 18) months will be presented.

A subgroup analysis may be conducted comparing OS in the following subgroups, assuming sufficient sample size per subgroup: platinum therapy receiving (carboplatin or cisplatin), age ( $\geq 65$ ,  $< 65$ ), gender, performance status, smoking status, CNS metastasis at baseline (Yes/No) and number of chemotherapy cycles (5 or 6 cycles vs 4 or less cycles)

For each subgroup, the HR and 95% CI will be calculated by Cox regression and a log-rank test will be provided.

- Time to Treatment Discontinuation (TTD): Summaries for the TTD will be provided (continuous data).

### 5.2.2 Secondary outcome 2

To describe the impact of durvalumab in combination with platinum–etoposide as first-line treatment for patients with ES-SCLC on patients' disease-related symptoms and Health Related Quality of Life (HRQoL) and (PROs).

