1. PROTOCOL SUMMARY

1.1 Schedule of activities (SoA)

The procedures for the screening and treatment periods in this study are presented in Table 1 and Table 2, and the procedures for the follow-up period are presented in Table 2. Patients who continue beyond Cycle 13 will continue with all Cycle 13 assessments until termination of treatment (Table 1).

Whenever vital signs and blood draws are scheduled for the same nominal time, the assessments should occur in the following order: vital signs and then blood draws. The timing of the vital signs assessments should be such that it allows the blood draw to occur at the timepoints indicated in the SoAs. Whenever electrocardiograms (ECGs), vital signs, and blood draws are scheduled for the same nominal time, the assessments should occur in the following order: ECG, vital signs, and then blood draws. The timing of the first 2 assessments should be such that it allows the blood draw to occur at the timepoints indicated in the SoAs.

For durvalumab

- Patients may delay dosing under certain circumstances.
 - Dosing may be delayed per the Dosing Modification and Toxicity Management Guidelines, due to either an immune or a non-immune-related AE.
 - If dosing must be delayed for reasons other than treatment-related toxicity, dosing will resume as soon as feasible.
 - Dosing intervals of subsequent cycles (during chemotherapy interval is 21 days, post chemotherapy interval is 28 days) may be adapted +/-3 days as clinically feasible in order to gradually align treatment cycles with the schedule of tumor efficacy (RECIST) and PRO assessments.

For EP treatment

- Patients may delay and subsequently resume dosing per local standard clinical practice.
 - If dosing must be delayed for reasons other than treatment-related toxicity, dosing will occur as soon as feasible.

Table 1 Schedule of assessments for durvalumab therapy treatment

		During Chemotherapy 1 cycle = 21 days				Post-Chemotherapy 1 cycle = 28 days				
	Screening	C1	C2	C3	C4-C6	C5-C7 to PD		End of treatment		
Week	-4 to -1	0	Q3w ±3 days during chemotherapy and q4w ±3 days post-chemotherapy, unless dosing needs to be held for toxicity reasons							
Day	-28 to -1	1 ^a	Q21days ±3 days during chemotherapy and q28days ±3 days post-chemotherapy, unless dosing needs to be held for toxicity reasons							For details, see Section
Informed Consent										
Informed consent: study procedures ^b	X								5.1	

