Consent: sample for biomarker analysis (optional)	X								5.1	
Study procedures										
Physical exam (full)	X								8.2.2	
Targeted physical exam (based on symptoms)		X	X	X	X	X		X	8.2.2	
Vital signs ^c	X	X	X	X	X	X		X	8.2.3	
ECG ^d	X	As clinically indicated							8.2.4	
Concomitant medications	<----->								6.4	
Demography, including baseline characteristics and tobacco use	X								5.1	
Eligibility criteria	X								5.1, 5.2	
Laboratory Assessments										
Clinical chemistry ^e	X	X ^f	X	X	X	X		X	Table 8	
Hematology ^e	X	X ^f	X	X	X	X		X	Table 9	
TSH ^g , (reflex free T3 or free T4 ^h)	X	X	X	X	X	X		X	Table 8	
Urinalysis	X	As clinically indicated							Table 10	
Hepatitis B and C and HIV	X								8.2.1	

		During Chemotherapy 1 cycle = 21 days				Post-Chemotherapy 1 cycle = 28 days			
	Screening	C1	C2	C3	C4-C6	C5-C7 to PD	End of treatment		
Week	-4 to -1	0	Q3w ±3 days during chemotherapy and q4w ±3 days post-chemotherapy, unless dosing needs to be held for toxicity reasons						For details, see Section
Day	-28 to -1	1 ^a	Q21days ±3 days during chemotherapy and q28days ±3 days post-chemotherapy, unless dosing needs to be held for toxicity reasons						
Efficacy evaluations									
Tumor assessments (RECIST 1.1) ^q	X	On-study tumor assessments will be performed following local standard practice, but at least with a maximum interval of 12 weeks. It is recommended that on-study tumor assessments occur q9w ± 1w for the first 12-18 weeks (relative to the C1D1, during chemotherapy treatment), and then, at least with a maximum interval of 12 weeks if signs or symptoms of progression do not happen before, if it is the standard procedure at study site, until RECIST 1.1-defined radiological progression plus an additional follow-up scan 4-8 weeks later. ^s						8.1, E	

^a Every effort should be made to minimize the time between inclusion and starting treatment (ie, within 1 day of inclusion).

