#### 4.1.2 Overall design

Durvalumab will be concurrently administered with first-line chemotherapy (EP) on every 3-week (q3w) schedule for 4 to 6 cycles, and will continue to be administered post-chemotherapy on an every 4 week (q4w) schedule until confirmed progressive disease (PD) or unacceptable toxicity.

Durvalumab + chemotherapy combination:

- Durvalumab 1500 mg via IV infusion q3w concurrently with chemotherapy, starting on Week 0, for 4-6 cycles. If a patient 's weight falls to 30 kg or below ( $\leq 30$  kg), then the patient should receive weight-based dosing equivalent to 20 mg/kg of durvalumab after consultation between the Investigator and Study Physician, until the weight improves to above 30 kg ( $> 30$  kg), at which point the patient should start receiving the fixed dosing of durvalumab 1500 mg.
- EP: the dose of etoposide + carboplatin or cisplatin investigated will not exceed the product label dose for the given indication dose (etoposide [80 to 100 mg/m^2] via IV infusion with either carboplatin [area under the curve (AUC) 5-6] via IV infusion or cisplatin [75 to 80 mg/m^2] via IV infusion), starting on Week 0, for 4-6 cycles.

Durvalumab monotherapy:

- Durvalumab 1500 mg via IV infusion q4w, starting 3 weeks after the last infusion of the combination, until confirmed progressive disease (PD) or unacceptable toxicity. If a patient 's weight falls to 30 kg or below ( $\leq 30$  kg), then the patient should receive weight-based dosing equivalent to 20 mg/kg of durvalumab q4w after consultation between Investigator and Study Physician, until the weight improves to above 30 kg ( $> 30$  kg), at which point the patient should start receiving the fixed dosing of durvalumab 1500 mg q4w.

Unless specific treatment discontinuation criteria are met, patients will continue therapy until clinical progression or confirmed radiological progression.

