#### Endpoints analyzed:

- Progression-free survival (PFS): This analysis will be performed for the Intention-to-Treat population (ITT). PFS is defined as the time from the first date of treatment until the date of objective disease progression or death (by any cause in the absence of progression) regardless of whether the patient withdraws from IP or receives another anticancer therapy prior to progression.

**PFS (days)** = Date of event or Censor date – treatment start date +1

Patients who have not progressed or died at the time of analysis will be censored at the time of the latest date of assessment from their last evaluable assessment. However, if the patient progresses or dies after 2 or more missed visits, the patient will be censored at the time of the latest evaluable assessment prior to the 2 missed visits. If the patient has no evaluable visits or does not have baseline data, he/she will be censored at Day 1 unless he/she dies within 2 visits of baseline, in which case the date of death is the event date.

The PFS analysis will be based on the programmatically derived RECIST 1.1 using the Investigator tumor assessments. It will be analysed PFS, PFS at 6 months (6mPFS) and PFS at 12 months (12mPFS).

- Objective response rate (ORR): This outcome will be analysed for the responder's analysis set. The ORR will be based on the programmatically derived RECIST 1.1 using the investigator tumor data.
- Duration of response (DoR): This outcome will be analysed for the responder's analysis set. DoR is defined as the time from the date of first documented response per RECIST1.1 until the first date of documented progression per RECIST1.1 or death in the absence of disease progression.

DoR (days) = Date of PFS event or censoring – Date of first response +1

The end of response should coincide with the date of progression or death from any cause used for the PFS endpoint. If a patient does not progress following a response, then the patients' DoR will be censored at the PFS censoring time. DoR will not be defined for those patients who do not have a documented response. It will be analysed DoR and DoR at 1 year (DoR12)

- Overall survival (OS): This analysis will be performed for the Intention-to-Treat population (ITT). OS is defined as the time from the first date of treatment until death due to any cause.

OS (days) = Death date or Censor date - treatment start date +1

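### If run, the PFS and OS comparison by chemotherapy cycles received (5–6 vs 4 or fewer), timed from first dose, carries immortal-time bias towards 5–6 cycles

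*SAP*

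**What the plan says.** SAP 5.2.1 lists platinum agent, age, gender, performance status, smoking and CNS metastasis as factors for optional subgroup comparisons of PFS and OS, subject to sufficient sample size. It adds one factor that is not known at baseline: "number of chemotherapy cycles (5 or 6 cycles vs 4 or less cycles". The same method serves all of them: "For each subgroup, the HR and 95% CI will be calculated by Cox regression and a log-rank test will be provided". The subgroup lists in Protocol 9.5.1 and 9.5.2.2 do not contain cycle number.

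Both clocks start at first dose (SAP 4.2.2.1): "PFS is defined as the time from the first date of treatment until the date of objective disease progression or death", and "OS is defined as the time from the first date of treatment until death due to any cause".

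On timing, SAP 4.1.2 states: "Durvalumab will be concurrently administered with first-line chemotherapy (EP) on every 3-week (q3w) schedule for 4 to 6 cycles". Protocol Table 1 sets the window as "Q21days ±3 days during chemotherapy and q28days ±3 days post-chemotherapy", and for chemotherapy Protocol 1.1 adds: "Patients may delay and subsequently resume dosing per local standard clinical practice". SAP 4.3.4.1 counts EP cycles as received; no number of planned cycles is fixed at baseline. Neither document gives a landmark, a time-dependent covariate or delayed entry for this comparison.

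**The concern.** A patient enters the 5–6 group only by staying alive, and in most cases progression-free, long enough to start cycle 5. Time from first dose to that point is credited to the 5–6 group although its members could not have died in it. Deaths during those weeks all go to the other group. For OS this is strict. For PFS it is nearly so: the Protocol synopsis lets clinically stable patients continue treatment after a first RECIST progression, so a few may progress early and still reach cycle 5.

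Protocol 4.3.1.3 allows up to six combination cycles where CASPIAN allowed four. A hazard ratio below 1 for 5–6 cycles could therefore be read as evidence for longer chemotherapy when part or all of it comes from how the groups were formed.

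**Working it through.** The documents give no hazard ratio, event count or power for this comparison, so there is no plan figure to reproduce. Everything below assumes that extra cycles have no effect.

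**Earliest cycle 5.** Four intervals of 21 days give 4 × 21 = 84 days, or 84 / 30.4375 = 2.76 months. Even if every interval used the full −3 days, 4 × 18 = 72 days remain.

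**Events before week 12, constant hazard:** 1 − 0.5^(2.76 / median).
- Time to progression, medians 4, 5 and 6 months (Protocol 2.3.3, quoted there for earlier chemotherapy): 38%, 32% and 27%. At a 5-month median that is 0.318 × 85 ≈ 27 patients.
- OS, medians 10.3 and 13.0 months (Protocol 2.3.1.2): 17% and 14%. At 13.0 months that is 0.137 × 85 ≈ 12 deaths.

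**OS shaped as in CASPIAN.** Protocol 2.3.3 gives 53.7% alive at 12 months and 33.9% at 18 months. A Weibull curve through both points has
- shape = ln[ln(1/0.339) / ln(1/0.537)] / ln(18/12) = 1.37
- scale = 12 / [ln(1/0.537)]^(1/1.37) = 17.0 months
- median 13.0 months, matching Protocol 2.3.1.2
- 8.0% dead by day 84 (0.080 × 85 ≈ 7 patients) and 10.7% by day 105.

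**Simple simulation.** Exponential times, n = 85, censoring uniform over 12–18 months (from the study dates in Protocol 1.2). A fixed share of those event-free at day 84 goes on to 5–6 cycles.

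| Endpoint, median | 30% go on | 50% | 70% |
|---|---|---|---|
| PFS, 4 months | 0.57 | 0.49 | 0.38 |
| PFS, 5 months | 0.60 | 0.52 | 0.40 |
| PFS, 6 months | 0.62 | 0.54 | 0.43 |
| OS, 10.3 months | 0.69 | 0.61 | 0.48 |
| OS, 13.0 months | 0.70 | 0.62 | 0.50 |

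A day-84 landmark gives 0.98–1.02 throughout. At a 5-month PFS median and 50% share, if 25% or 50% of those intended for 5–6 cycles who progress early still reach cycle 5, the naive PFS value moves to 0.62 or 0.74.

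**Fuller simulation.** Assumptions:
- Median time to progression (or, in the second model, to first event) 5 or 6.5 months.
- Two models of OS: the Weibull above, independent of progression; or death mainly after progression, with median OS 13 months.
- Scans at weeks 9 and 18 then every 12 weeks, or every 12 weeks throughout. Protocol Table 1 sets only an upper limit: "On-study tumor assessments will be performed following local standard practice, but at least with a maximum interval of 12 weeks".
- Cycle 5 on day 84 or up to 3 weeks later. After detected progression it is given never, or at 30% of the usual rate.

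| Share of eligible patients going on | PFS HR | OS HR |
|---|---|---|
| 30% | 0.62–0.84 | 0.63–0.85 |
| 50% | 0.54–0.79 | 0.57–0.81 |
| 70% | 0.44–0.70 | 0.48–0.76 |

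Where OS is independent of progression, the 50% OS value is about 0.8; lower values come from the model linking death to progression. A week-15 landmark in patients alive and progression-free, grouped by cycles started by then, gives 0.98–1.02 for PFS and 0.97–1.03 for OS.

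No false-positive rates are given for PFS. Progressions tie on scan dates, so those rates depend on using the standard tie-corrected log-rank variance and would have to be computed that way.

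**The case against.** The comparison is optional and secondary. The study has no formal hypotheses (Protocol 9.1), and Protocol 4.3.1.3 justifies six cycles by flexibility and the need for safety data, not by an efficacy contrast. This limits the weight of the point. But if the comparison is run, the SAP fixes the method, and a descriptive label does not remove bias from a hazard ratio and a test.

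The inputs are also open to challenge. The assumed 5–6.5 months is not the Protocol's 4–6 months, which describes earlier treatment, and the share reaching cycle 5 is unknown. The simple simulation covers 4–6 months and shows a larger bias, so the sign does not hang on this choice. The size does, and for OS the bias may be modest.

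A reader might infer more than the documents support:
- *That the reported hazard ratio must favour 5–6 cycles, or cannot be interpreted at all.* Only the immortal-time component has a fixed direction. The simulations choose at random who goes on among eligible patients, apart from the reduced rate after detected progression. In practice response, toxicity and investigator choice decide, and that confounding could act either way.
- *That duration of response and ORR by cycle number are biased to the same extent.* If first response is documented at a week-12 scan, duration of response has essentially no immortal time before an on-schedule cycle 5. For ORR, early response may itself influence cycle number, which is a different problem. No size is claimed for either.

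**Conclusion.** The comparison is wrong as written for PFS and OS: it treats a post-baseline quantity as a baseline factor and times it from first dose, which builds in bias towards 5–6 cycles. With no true effect, no confounding, CASPIAN-shaped OS, the assumed 5–6.5 months to progression and half of eligible patients going on, the hazard ratio is about 0.54–0.79 for PFS and 0.57–0.81 for OS. Varying that share from 30% to 70% widens this to 0.44–0.84 and 0.48–0.85. The direction of this component held in every scenario examined; the size is illustrative. The correction should be made, but it concerns one optional secondary analysis.

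**What to change.** In SAP 5.2.1, take cycle number out of the ordinary subgroup list for PFS and OS and do one of the following.

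- Prespecify a landmark analysis, for example at week 15, which leaves room for the visit window and for delays. For both endpoints include only patients alive and progression-free at the landmark, count time from there, and group by cycles started by then. Requiring survival alone is not enough for OS: where death follows progression, that version still gives 0.62–0.88 over shares of 30–70%. Grouping by final count is not enough either: with delays of up to 3 weeks, a week-12 landmark grouped that way falls as low as 0.94 for PFS and 0.90 for OS.
- Or report cycle number descriptively, with no hazard ratio or p-value.

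Label any result as post-baseline and confounded by indication, which a landmark does not remove. Report duration of response and ORR by cycle number descriptively only.

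The cost is SAP wording and minor programming. Patients who have died or progressed by week 15 leave this one comparison: 17–39% with CASPIAN-shaped OS and 33–44% with constant hazards, so between 0.17 × 85 ≈ 14 and 0.44 × 85 ≈ 37 patients. Its confidence interval widens accordingly.

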During the treatment period, patients who are clinically stable at an initial RECIST 1.1-defined PD may continue to receive study treatment at the discretion of the Investigator and patient. A follow-up scan is to be collected after the initial RECIST 1.1-defined PD, preferably at the next (and no later than the next) scheduled imaging visit, and no less than 4 weeks after the prior assessment of PD and this scan is evaluated using the Confirmation of Radiological Progression criteria are outlined in Appendix E. If the subsequent scan does not confirm the immediate prior radiological PD, scanning should continue until the next RECIST 1.1-defined PD which in turn will require a subsequent scan evaluated using the Confirmation of Radiological Progression criteria outlined in Appendix E.

Follow up of patients post discontinuation of study drug

Patients who have discontinued treatment due to toxicity or symptomatic deterioration, clinical progression, or who have commenced subsequent anticancer therapy will be followed up with tumor assessments until RECIST 1.1-defined PD plus an additional follow-up scan or until death (whichever comes first) and followed for survival.

Survival

All patients in the study should be followed up for survival.

Statistical methods

All statistical analyses will be performed by AstraZeneca or its representatives (e.g. CRO).

A comprehensive statistical analysis plan (SAP) will be prepared and finalized within 3 months of the first enrolled patient, and any subsequent amendments will be documented, with final amendments completed prior to reporting of the data.

All analyses will be descriptive in nature. Categorical (e.g., gender) study measures will be reported using frequency and proportions and continuous measures (e.g., age) will be reported using mean, median, standard deviation and range. Additionally, Kaplan-Meier curves will be presented for time-to-event outcomes such as overall and progression free survival.

All analyses will be based on the intention to treat (ITT) population consisted of all enrolled patients who had received at least 1 dose of study drug (chemotherapy or Durvalumab). For the overall study population and for any subpopulation, estimated 95% CIs for various event rates will be calculated.

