9.1 Statistical hypotheses

There is no formal hypotheses in this study.

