9.5.2.2 Efficacy variables

Efficacy data will be reported for patients overall. Results of all statistical analysis will be presented using a 95% confidence interval (CI), unless otherwise stated.

The following table (Table 13) details which endpoints are to be subjected to statistical analysis.

Table 13 Pre-planned statistical and sensitivity analyses to be conducted

Endpoints analyzed	Notes
Progression-free survival	Analysis by Kaplan Meier estimates using Investigator RECIST 1.1 assessments
Objective response rate	Analysis using Investigator RECIST 1.1 assessments
Duration of response	Analysis by Kaplan Meier estimates using Investigator RECIST 1.1 assessments, in patients with documented response
PFS at 6 and 12 months	Using the Kaplan Meier estimates of progression free survival at 6 and 12 months
Overall survival	Analysis by Kaplan Meier estimates
Overall survival at 6, 12 and 18 months	Using the Kaplan Meier estimates of OS at 6, 12 and 18 months
Time to deterioration (EORTC QLQ-C30 and QLQ-LC13 endpoints)	Analysis by Kaplan Meier estimates. Change from baseline values will be calculated.

EORTC European Organisation for Research and Treatment of Cancer; QLQ-C30 v3 30-item Core Quality of Life Questionnaire, version 3; QLQ-LC13 13-item Lung Cancer Quality of Life Questionnaire;

RECIST 1.1 Response Evaluation Criteria in Solid Tumors, version 1.1.

Progression-free survival

The PFS analysis will be based on the programmatically derived RECIST 1.1 using the Investigator tumor assessments. The analysis will be performed using Kaplan Meier plots. Summaries of the number and percentage of patients experiencing a PFS event will be provided along with median PFS and its 95% confidence interval. In addition, the proportion of patients who are progression-free at 6 and 12 months will be presented.

A subgroup analysis may be conducted comparing PFS in the following subgroups, assuming sufficient sample size per subgroup: platinum therapy receiving (carboplatin or cisplatin), age, gender, performance status, smoking status and CNS metastasis at baseline (Y/N).

Other baseline variables may also be assessed if there is clinical justification. The purpose of the subgroup analyses is to assess the consistency of treatment effect across expected prognostic and/or predictive factors.

For each subgroup, the HR and 95% CI will be calculated by Cox regression and a log-rank test will be provided.

Objective response rate

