## **6.3 Adjustment for multiple comparisons**

Not applicable.

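### SAP 5.2.1 allows up to 28 subgroup significance tests that serve no stated hypothesis, and SAP 6.3 gives no rule for reading them

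*SAP*

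**What the plan says.** SAP 5.2.1 repeats one list of seven subgroup factors under each of PFS, ORR, DoR and OS: platinum agent, age split at 65, and five more ("gender, performance status, smoking status, CNS metastasis at baseline (Yes/No) and number of chemotherapy cycles (5 or 6 cycles vs 4 or less cycles"). For PFS, DoR and OS the instruction is "For each subgroup, the HR and 95% CI will be calculated by Cox regression and a log-rank test will be provided". For ORR it is "Results will be compared using Chi-Squared test". All of this is conditional; for ORR, for example, "A subgroup analysis may be conducted comparing ORR in the following subgroups, assuming sufficient sample size per subgroup". No threshold for a sufficient sample is given. SAP 6.3, headed "Adjustment for multiple comparisons", says only that the matter does not apply.

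The protocol synopsis states "All analyses will be descriptive in nature", and Protocol 9.1 states "There is no formal hypotheses in this study". Protocol 9.5.2.2 nevertheless attaches Cox and log-rank comparisons on six of these factors to PFS and OS. Under PFS it adds "Other baseline variables may also be assessed if there is clinical justification".

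**The concern.** A study with no hypothesis has nothing for a between-group significance test to decide, yet the plan provides for such tests, and the SAP more than doubles the protocol's number. Neither document calls these tests exploratory or nominal, although the protocol uses the word exploratory elsewhere, for the health-economic and biomarker analyses. A reader of the final report would meet a set of subgroup p-values with no guidance on how many were looked at or what a small one means.

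The study is meant to inform treatment decisions in patients such as those with ECOG PS 2, who are capped at 30% of recruitment (0.30 x 85 = 25.5, so about 25 patients). Unlabelled p-values in groups of that size are easily misread, whether small or large.

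**Working it through.** **The plan's own figures.** No alpha, power or error rate is given for these tests. The only design figures are the exact 95% intervals for AE incidence at n = 85 in Protocol 9.2. They reproduce (17/85: 12.1 to 30.1; 21/85: 16.0 to 35.3; 51/85: 48.8 to 70.5; 60/85: 59.7 to 80.0) but do not bear on subgroups.

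**Inputs.**
- Factors and endpoints: 7 and 4 (SAP 5.2.1); 6 and 2 (Protocol 9.5.2.2).
- Sample size: about 85 (Protocol 9.2).
- Alpha: assumed 0.05 two-sided, to match the 95% intervals in Protocol 9.5.2.2. The only explicit threshold, also 0.05 two-sided, is in Protocol Appendix K and belongs to a biomarker sub-study.
- Each factor is counted as one two-group comparison.

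**Count.** SAP: 7 x 4 = 28 (21 log-rank, 7 chi-squared). Protocol: 6 x 2 = 12. The SAP adds 28 - 12 = 16: number of cycles for PFS and OS (2), ORR (7) and DoR (7). The PRO log-rank tests in SAP 5.2.2 are not counted, and the safety subgroups in SAP 5.1 carry no test.

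**Chance of at least one p<0.05 when no factor matters, independent tests:** 1 - 0.95^k.
- k = 28: 1 - 0.95^28 = 76.2%; expected number of false positives 28 x 0.05 = 1.4
- k = 12 (protocol only): 46.0%
- k = 7 (one endpoint only): 30.2%

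**Related endpoints.** The four endpoints come from the same patients, so independence overstates the figure. A simulation with 85 patients and no true associations (3,000 runs per setting) tested seven independent binary factors on all four endpoints. Its assumed inputs were subgroup shares of 15% to 50%, median time to progression 5.5 months, median OS 13 months, ORR 68% and censoring at 12 to 18 months.

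| Latent correlation among progression, death and response | At least one of 28 below 0.05 |
|---|---|
| 0 | 73% |
| 0.3 | 72% |
| 0.6 | 69% |
| 0.9 | 66% |

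If the four endpoints were perfectly correlated within each of seven independent factors, there would in effect be seven tests, giving the floor of 30.2%. Lower values need strong correlation between different factors as well: a common correlation of 0.5 across all 28 tests gives 49%, and 0.8 gives 25%. Correlation that high between, say, sex and platinum agent is not realistic.

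**Number of cycles.** This factor is fixed after treatment starts. Four 3-weekly cycles take 12 weeks (12 x 7 / 30.4 = 2.8 months), so a patient who progresses or dies before then is unlikely to reach a fifth. In the simulation at correlation 0.6, allowing 5 or 6 cycles only when PFS exceeded 2.8 months made this factor significant on at least one endpoint in 91% of runs, against 17% when it was assigned at random. The any-of-28 figure rose from 69% to 97%. That is survivorship bias; a stricter alpha does not remove it.

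**The case against.** The best defence is that nothing here needs controlling. The analyses are declared descriptive, no decision rests on a subgroup, every comparison is optional, and an undefined sample-size condition can only bring the number below 28. Protocol 9.5.2.2 also gives the subgroups a purpose, consistency of effect across expected prognostic or predictive factors. By that account some differences are expected to be real. This explains why formal alpha control was left out, and I would not ask for it. It does not explain why tests are there at all, and a single-arm study cannot show whether a treatment effect is consistent across subgroups, only whether outcome differs between them.

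Several stronger readings are tempting, and the documents do not support them:
- That a spurious subgroup finding is to be expected. This needs an alpha the documents do not state, most or all of the 28 tests run, and no true associations; performance status is a plausible real prognostic factor.
- That the set of factors is open-ended. The clause on other baseline variables stands once, under PFS in the protocol, and requires clinical justification. The SAP list is fixed.
- That the synopsis leaves out platinum agent or number of cycles. The synopsis list has a visible gap in the text, so nothing can be said about what is absent. It can be said that it names liver metastases and PCI, which the SAP list does not.
- That brain metastases are part of the stated rationale. The rationale names PS 2, prior chemoradiotherapy for limited-stage disease, stable comorbidities, controlled autoimmune disease and expected benefit from PCI.
- That deleting p-values lowers the error rate. A 95% interval that excludes no difference carries essentially the same information as p<0.05. What helps is the rule on how intervals may be read.

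**Conclusion.** The point stands as a minor one. Up to 28 subgroup significance tests are permitted in a study that declares itself descriptive and without hypotheses, and the SAP gives no rule for interpreting them. The inconsistency is already inside the protocol (12 tests), and the SAP enlarges it. The 76%, the 66% to 73% and the 30% floor assume 0.05 two-sided, all 28 tests run and no true association, so they mark the upper range of the problem and do not forecast it. The primary endpoints, grade 3 or higher AEs and imAEs, are not affected. Number of chemotherapy cycles is a separate weakness that no multiplicity method would repair.

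**What to change.** 1. In SAP 5.2.1 and Protocol 9.5.2.2, remove the subgroup log-rank and chi-squared tests. Report each subgroup's Kaplan-Meier estimate or ORR, and the HR or difference, with 95% CIs.
2. Replace the entry in SAP 6.3 with wording such as: *Subgroup comparisons are exploratory. Intervals are unadjusted and are not to be read as tests; an interval that excludes no difference is not a claim of significance. The number of comparisons made is reported with the results.*
3. Use one subgroup list in the synopsis, Protocol 9.5 and SAP 5, settling whether liver metastases and PCI belong in it.
4. Take number of chemotherapy cycles out of the ordinary subgroup list. If it is reported, describe it separately and say that patients had to remain on treatment to reach five or six cycles. PCI, which the protocol allows only after a response, needs the same caution.

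Cost: a few lines in the SAP and a matching protocol clarification, with no new data or patients. The downside is fewer p-values to quote.
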